3.0 Inclusion and Exclusion Criteria

[figure not shown]
3.1 Screening for Eligibility

PROTOCOL TITLE: Designing with Dissemination in Mind: Optimization of a mHealth Physical Activity Intervention for Breast Cancer Survivors (Fit2Thrive)

This study will have two phases (see Figure 4). Phase 1 (Aim #1) will involve intervention development. Phase 2 (Aims #2, #3 and Exploratory) will involve the pilot testing of the intervention components to be identified in Aim #1.

Phase 1 and Phase 2. For both phases, interested participants will be screened for eligibility either via an on-line screening questionnaires or telephone interview. Eligible breast cancer survivors will be offered the opportunity to participate and will complete informed consent.

Figure 4. Summary of Phase 1 and 2 of Research Protocol

3.2 *Inclusionary and Exclusionary Criteria*

This study will have two phases (see Figure 3). Phase 1 (Aim #1) will involve intervention development. Phase 2 (Aims #2, #3 and Exploratory) will involve the pilot testing of the intervention components to be identified in Aim #1.

Breast Cancer Survivors in Phase 1 and 2. The same inclusionary criteria for breast cancer survivors will be used for all phases of the research. However, all women recruited into the intervention in Phase 2 will also be required to pass the *Physical Activity Readiness Questionnaire (PAR-Q)*⁹⁶ (see attached) or receive medical clearance from their primary care physician or oncologist.

Inclusionary Criteria for Breast Cancer Survivors:

- Women \geq 18 years of age who were diagnosed with Stage I-III breast cancer within the last 5 years
- Have completed last cancer treatment (adjuvant chemotherapy, radiation therapy or surgery) at least 3 months prior to enrollment
- English speaking
- Currently participate in <60 minutes of moderate and vigorous PA/week (Phase 2 only)

PROTOCOL TITLE: Designing with Dissemination in Mind: Optimization of a mHealth Physical Activity Intervention for Breast Cancer Survivors (Fit2Thrive)

- Own a smartphone (For Phase 2 only: iPhone –version 5 or greater or an Android –version 5 or greater)
- Have access to a computer with Internet
- Participants may be using adjuvant endocrine therapies.
- Willing to be waitlisted for future wave if current wave reaches capacity (Phase 2 only)

Exclusionary Criteria for Breast Cancer Survivors:

- Women will be excluded if they report any of the following:
 - Respiratory, joint or cardiovascular problems precluding PA
 - Metastatic disease
 - Planned elective surgery during duration of the intervention/follow-up that would interfere with participation (e.g., breast reconstructive surgery).
 - ONLY IF PARTICIPATING IN OPTIONAL DBS COLLECTION:
 - A prior cardiovascular event (i.e. stroke, myocardial infarction)
 - Have been diagnosed with an acute or chronic immune system medical conditions, or conditions that impact immune and endocrine function (e.g., CFS, Lupus, rheumatoid arthritis, Hepatitis C, or immunosuppressive treatment requiring conditions)

Inclusionary Criteria for Other Stakeholders in Phase 1:

- English-speaking
- Have expertise in breast cancer or physical activity OR organization the individual works for actively works with breast cancer survivors on a regular basis
- Own a smartphone

Inclusionary Criteria for “Buddies”:

- Must be at least 18 years old
- Have access to a computer and internet
- Own a smartphone
- Be willing to receive regular emails from the study team
- Be willing to wear a Fitbit and transmit Fitbit data to the study team
- Be willing to “friend” participant in the Fitbit app and provide support and encouragement to the participant.

3.3 *High-risk Subpopulation Inclusion.*

The following subgroups will be excluded from the present study:

- Adults unable to consent
- Individuals who are not yet adults (infants, children, teenagers)
- Pregnant women
- Prisoners

4.0 Study-Wide Number of Subjects:

Phase 1. We will recruit stakeholders including breast cancer survivors (n=30 for interviews; up to 100 for usability testing), experts and clinicians (n=10-15; e.g.

PROTOCOL TITLE: Designing with Dissemination in Mind: Optimization of a mHealth Physical Activity Intervention for Breast Cancer Survivors (Fit2Thrive)

oncologists, nurses, experts in D&I, PA and rehabilitation) and representatives (n=10-15) from local community organizations (e.g. Gilda's Club Chicago, the YMCA and American Cancer Society Illinois Chapter).

Phase 2. We plan to accrue a nationwide sample of 256 women to the intervention pilot testing phase. Approximately 50% of these will be assigned to the buddy condition. As such we will accrue 128 buddies. We anticipate 80% of these "buddies" (n=102) will agree to participate in the optional questionnaire assessments. We will recruit up to 35 participants for the post-intervention interviews.

5.0 Study-Wide Recruitment Methods:

5.1 *When, where and how potential subjects will be recruited.*

Phase 1. Women will be recruited from the Army of Women (AOW) e-blast.[©] The AOW is an online initiative that connects breast cancer researchers with women who are willing to participate in research. The database currently consists of ≥375,000 women. Of these, ~30% (112,500) self-report a breast cancer history. Women interested in participating in the current study will respond to the e-blast consenting to have their contact information released by the AOW to study investigators. Their contact information will, then, be forwarded to the study investigator who will provide a description of the study and further screen for eligibility either via on-line screening questionnaires or telephone interview. Eligible breast cancer survivors will be offered the opportunity to participate and will complete informed consent.

Community representatives will be recruited in conjunction with NU's Center for Community Health (led by Co-I [name]) via personalized e-mails and phone calls. Experts will be recruited through the RHLCCC and the PI's, co-investigators' professional networks via listservs and personalized e-mails and phone calls.

Phase 2. Breast cancer survivors will be recruited through an e-blast sent to members of the Army of Women[©], an online initiative that connects breast cancer researchers with women who are willing to participate in research. The database currently consists of ≥375,000 women and men. Of these, ~30% (112,500) self-report a breast cancer history. Women interested in participating in the current study will respond to the e-blast. Their contact information will be forwarded to the study investigator who will provide a description of the study and further screen for eligibility either via on-line screening questionnaires or telephone interview. Eligible breast cancer survivors will be offered the opportunity to participate and will complete informed consent.

If our recruitment goals are not being sufficiently met via the Army of Women[©] we will also post study fliers and advertisements on social media sites (i.e. Facebook, PatientsLikeMe) and on-line forums (i.e. Sisters Network, Nueva Vida, Living Beyond Breast Cancer). In addition we will send recruitment emails to all women from previous studies who consented to being contacted regarding future study opportunities. All women who are recruited through these alternative strategies will be instructed to contact

PROTOCOL TITLE: Designing with Dissemination in Mind: Optimization of a mHealth Physical Activity Intervention for Breast Cancer Survivors (Fit2Thrive)

the study staff who will provide a description of the study and further screen for eligibility either via on-line screening questionnaires or telephone interview. Eligible breast cancer survivors will be offered the opportunity to participate and will complete informed consent.

- **Buddy recruitment:** Breast cancer survivors assigned to the Buddy component, will be asked to contact their buddy and provide the study team with the name and email address of their chosen buddy. The buddy will then be emailed a brief description of the study and a link to the on-line buddy screening RedCap. Interested and eligible buddies will be offered the opportunity to participate and will complete informed consent. If a buddy indicates, they are not interested or fails to respond after 3 contact attempts, we will ask the participant for a new buddy name and email address.
- **Post-intervention interview:** Individuals who participated in the Fit2Thrive intervention within the previous 6 months and agreed to hear about future studies will be eligible. Women will be invited to participate via email. They will be selected for invitation based on adherence to the program and intervention component assignment to ensure broad representation. Former participants will be contacted up to 3 times to participate after which we will cease contact.

5.2 *Methods used to identify potential subjects.*

Women who meet the following criteria will be included in the present study: a) indicate they are interested in the present study, b) meet all eligibility criteria and c) consent to participation.

“Buddies” who meet the following the following criteria will be included in the present study:) indicate they are interested in the present study, b) meet all eligibility criteria and c) consent to participation.

5.3 *Recruitment materials.*

All recruitment materials will list study eligibility criteria and requirements, will provide a link to the study web-page and will not deviate from the IRB-approved language. The posting will also include a phone number and study e-mail address where participants can reach staff if they have any general questions regarding study participation.

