7.3 Estimated date for study completion: June 30, 2020

8.0 Study Endpoints

8.1 Describe the primary and secondary study endpoints.

Primary study endpoint: intervention feasibility/acceptability.

Feasibility: This will be measured during the intervention, immediately post-intervention and after the follow-up period. Measures include:

- *Intervention reach:* # of participants enrolled/# of eligible individuals
- *Participant retention:* # of participants who drop out/# of participants randomized

PROTOCOL TITLE: Designing with Dissemination in Mind: Optimization of a mHealth Physical Activity Intervention for Breast Cancer Survivors (Fit2Thrive)

- *Intervention Adherence:* % of weeks adhered to exercise prescription during intervention period
- *Intervention Maintenance:* % of weeks adhered to exercise prescription during follow-up period
- *Intervention component engagement:*
 - During intervention: # of times, on average, participants interacted with each intervention component during intervention
 - During follow-up: # of times, on average, participants interacted with each intervention component during follow-up
 - Total: # of times, on average, participants interacted with each intervention component over intervention and follow-up

Acceptability: This will be measured via a process evaluation immediately post-intervention at 12 weeks and after the follow-up period at 24 weeks. This evaluation will assess the following:

- Perceived effectiveness of intervention components/app; use of app/intervention materials; plans to continue PA/app use; elements of intervention liked/disliked; satisfaction with program delivery, assessments and staff

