Women who express an interest in participating in the Fit2Thrive intervention via the Army of Women® will be sent an email with a brief study description and eligibility criteria. This email will also contain a link to the on-line (RedCap) Screening. The first part of the screening will provide an in-depth overview of the study. After viewing these materials, potential participants will first confirm interest in research participation and proceed to complete screening questions assessing for eligibility criteria (e.g., demographics, cancer diagnosis, age). After an individual passes the initial screening, they will automatically be redirected to complete the Physical Activity Readiness

Questionnaire (PAR-Q).⁹⁶ Once completed, they will provide detailed contact information and scheduling availability. Scored PAR-Q responses will be reviewed to determine if physician approval is required prior to participation. Those who require approval will be flagged for follow-up.

- **If not ineligible:** Participants will be thanked for their interest and directed to on-line resources for physical activity and nutrition for cancer survivors.
- **If eligible:** Participants will receive a study orientation call. Prior to this call, they will be sent a copy of the informed consent and a study overview handout.
- **Attempts to contact:** Study staff will make up to three email attempts to reach potential participants to complete the web screening. If unable to reach after the third attempt, study staff will mark the individual as “ineligible,” with the reason as “unable to contact.”

Recruitment Phone Call

Because participants will be recruited from all over the country, the orientation session will occur remotely via a telephone call. Prior to the call, study staff will email participants a copy of the informed consent and a study overview. During the call, study staff will

PROTOCOL TITLE: Designing with Dissemination in Mind: Optimization of a mHealth Physical Activity Intervention for Breast Cancer Survivors (Fit2Thrive)

[figure not shown]
introduce what is required for study participation and provide instructions for completing baseline assessments. If they failed PAR-Q screening, they will also be instructed that they will need to obtain physician consent prior to participation. This session will take approximately 10-15 minutes.

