- **If still interested:** Participants will be sent a link to the on-line consent form. If they failed PAR-Q screening, they will also be sent a link to a RedCap form to consent to allowing study staff to contact their physician and provide physician contact information.
- **If no longer interested:** They will be thanked and asked if they would be willing to be contacted regarding future study opportunities.
- **Attempts to contact:**
 - Study staff will make up to three call attempts to reach potential participants for the orientation call. If they are not reached at this point, staff will follow-up with one last call and email.
 - Study staff will make up to three e-mail attempts to reach potential participants to complete the informed consent. If unable to reach after the third attempt, study staff will call the participant and send one final email. Those who we are unable to reach after these attempts will be marked as “ineligible,” with the reason as “unable to contact.”

Assessments

After completion of informed consent, women will be e-mailed baseline study questionnaires via RedCap and notification that their accelerometer packet has been placed in the mail. The accelerometer packet includes: accelerometer, accelerometer instructions, accelerometer log, printed copy of the informed consent, a self-addressed stamped return envelope to return the accelerometer. Questionnaires will take approximately 30-45 minutes to complete and participants will be asked to complete the on-line study questionnaires within 10 days of receipt. They will be asked to wear the accelerometer for 7 consecutive days starting on the day indicated on the log and mail it back to study investigators at the end of the 7 days period.

Figure 5. Participant Flow Through Study

PROTOCOL TITLE: Designing with Dissemination in Mind: Optimization of a mHealth Physical Activity Intervention for Breast Cancer Survivors (Fit2Thrive)

Women will also have the option to participate in the self-collection of a 2.5 mL blood sample to be collected by pricking their finger with a retractable lancet and placing 5, 50 μ L spots of blood on a sample collection card. They will be mailed all materials needed to collect the blood spot (i.e. lancet, alcohol swab, band-aid) and written instructions with pictures for collecting and returning the sample as well as a self-addressed stamped envelope.

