Aim 2. Feasibility and acceptability will be evaluated using the measures detailed above. The primary hypotheses are: a) 75% of eligible survivors will agree to participate in the intervention; (b) enrollees will demonstrate engagement by monitoring PA on >80% of the study days and using one or more additional app components at least weekly. Descriptive analyses (means, frequencies) will be used to describe these results. Data from post-intervention interviews will be digitally recorded; digital files will be stored on a password-secured network drive. Recordings will be transcribed verbatim and de-identified. Three coders will independently review the de-identified transcripts, identify emergent themes, and assign initial codes using constant comparative analysis. This iterative process codes data based on identified conceptual themes. Data will be organized using qualitative data analyses software. Coders will meet often to discuss and refine the emerging themes, and triangulate their perspectives. Once a final coding structure is identified, coders will independently return to the transcripts to re-examine them and recode as necessary to ensure consistency. Disagreements will be resolved through deliberation and consensus. Analysis will identify both aides' and clients' perceptions of implementing the proposed intervention, strategies for tailoring the existing intervention content, and tactics for overcoming identified challenges to implementation.

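### Observed reach may be overstated against the 75% benchmark, because two rules class some non-participants as ineligible

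*Combined protocol and SAP*

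**What the plan says.** Section 8.1 states "Primary study endpoint: intervention feasibility/acceptability". The first feasibility measure listed there, and again in 9.4, is reach: the number "of participants enrolled/# of eligible individuals". Sections 1.2 and 11.1 (Aim 2) give the hypothesis that "75% of eligible survivors will agree to participate in the intervention", to be summarised descriptively.

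Eligibility for Phase 2 is set in 3.2. Beside the clinical, activity and technology criteria stands "Willing to be waitlisted for future wave if current wave reaches capacity (Phase 2 only". Section 5.2 includes only women who "meet all eligibility criteria and c) consent to participation".

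Section 9.2 codes women who stop responding at two stages:

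- **Screening** (web screening not completed): "If unable to reach after the third attempt, study staff will mark the individual as" ineligible, with inability to contact as the reason.
- **Recruitment Phone Call** (consent not completed): "Those who we are unable to reach after these attempts will be marked as" ineligible, with the same reason.

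A woman who says on the orientation call that she is no longer interested is thanked and asked about future contact. No ineligible code is given for her.

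**The concern.** Reach is meant to show what share of suitable women take up the programme. Willingness to wait for a later wave is a decision about taking part on the study's terms, not a clinical or technical attribute. As an inclusion criterion, it turns a refusal into ineligibility and removes it from the denominator.

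The consent-stage rule does the same to women who have already screened eligible. It also makes the count depend on how a woman drops out: the plan gives no ineligible code to one who says no, but it does to one who stops replying.

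The figure matters for two uses. Section 11.1 says the protocol will be refined before proceeding if feasibility benchmarks are missed. Section 2.3 describes the aim of the optimisation framework as public health impact, of which reach is one factor. An overstated reach would misinform both.

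**Working it through.** **Inputs**

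- Planned enrolment: "We plan to accrue a nationwide sample of 256 women to the intervention pilot testing phase" (4.0).
- Benchmark: 75% (11.1, Aim 2).
- Share *d* of otherwise eligible women removed by the two rules: not given in the plan, so assumed over a range that includes zero.

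**Starting point.** The plan gives no derivation of the 75% and no expected number of eligible women, so there is no calculation to reproduce. With 256 enrolled, 75% implies 256 / 0.75 = 341.3 women counted as eligible; 256 / 341 = 75.1%.

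**Effect of removal.** If *d* of otherwise eligible women are reclassified, the number removed is 341 × d / (1 − d). Reach with them counted is reported reach × (1 − d).

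| Assumed d | Women removed | Reach with them counted, from 256/341 | Same, from exactly 75% |
|---|---|---|---|
| 0% | 0 | 75.1% | 75.0% |
| 5% | 18 | 71.3% | 71.3% |
| 10% | 38 | 67.6% | 67.5% |
| 15% | 60 | 63.8% | 63.8% |

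**How few women matter.** Reach of 70% among all otherwise eligible women would be reported as 75% if d = 1 − 0.70 / 0.75 = 6.7%. That is 256 / 0.70 − 256 / 0.75 = 365.7 − 341.3, or about 24 women.

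**The opposite effect.** Women who accept wait-listing but are never offered a place, because accrual ends at 256, are eligible and not enrolled. Under the present definition they stay in the denominator and lower reach. As an illustration, 25 such women beside 341 others give 256 / 366 = 69.9%.

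**Which rules bear on the denominator.** The wait-list criterion and the consent-stage rule remove women who met, or would have met, every other criterion. The web-screening rule is different: those women never completed screening, so whether they were eligible is unknown.

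**The case against.** Willingness to wait and willingness to take part are not the same. A woman may want the programme now and be unable to accept a delay caused by the study's own wave capacity. Counting her as a non-participant records a capacity limit as a refusal. That is a fair argument for reporting reach both ways, but not for letting her drop out of the count unseen.

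Reach is also one of several feasibility measures and is analysed descriptively. Section 11.2 says sample size for the primary aims came from resources, so no error rate or power is affected, and no formal go/no-go rule rests on 75%. All of this stands and keeps the point minor.

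Three stronger readings are tempting, and the documents do not support them:

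- *The 75% is itself inflated.* It is a prospective hypothesis. The plan reports no observed reach; only a future observed value could be overstated against it.
- *The target will be met by definition, or the rules can only raise reach.* Three quarters of the women still counted as eligible must enrol. With no refusals or losses there is no effect, and wait-listed women never offered a place act in the other direction. The net bias cannot be settled from the plan.
- *The web-screening rule inflates reach in the same way.* Women of unknown eligibility do not belong in a count of eligible women. What they need is a separate category.

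**Conclusion.** The point holds as a minor weakness of definition. Read literally, sections 3.2, 5.2, 8.1 and 9.2 together remove wait-list refusers, and women lost at the consent stage, from the denominator of a primary feasibility measure. No other section adds them back or plans a second count.

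For these two routes the direction is upward whenever at least one woman is removed. The size is unknown: the fall of about 4 to 11 percentage points in the table rests wholly on an assumed 5% to 15% removed, and it is zero if none are. It depends on how many women decline or fall silent, and the plan gives neither figure.

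**What to change.** In 8.1 and 9.4:

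- Keep the wait-list condition as a scheduling requirement, but define the reach denominator as screened women who meet every criterion other than wait-list willingness.
- Count wait-list refusers, and women lost between eligible screening and consent, as eligible non-participants. This should cover women not reached for the orientation call, for whom 9.2 states no code.
- Put women who never completed web screening in a separate category of unknown eligibility.
- State how women who accept wait-listing but are never offered a place are handled.
- Report reach with and without each of these groups.

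The cost is one revised definition and a tally. Section 27.2 already keeps screening information for CONSORT reporting, so the recount is feasible provided that wait-list refusal and stage of loss are recorded as distinct reasons. The headline reach may come out somewhat less favourable.
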